### ***Pregnancy Counseling (Males and Females)***

Counseling about pregnancy precautions and the potential risks of fetal exposure must be conducted for all subjects at screening, Day 1 of every cycle during treatment, at treatment discontinuation and at the follow-up visit for all subjects. Please refer to Pomalidomide Pregnancy Risk Minimization Plan in [Appendix D](#).

### ***Pregnancy Testing for Females of Child Bearing Potential (FCBP)***

All FCBP must have 2 medically supervised negative serum or urine pregnancy tests (sensitivity of at least 25 mIU/mL) prior to starting the study. The first pregnancy test must be performed within 10-14 days prior to the start of study treatment and the second pregnancy test must be performed within 24 hours prior to the start of study treatment. The subject may not receive study drug until the study doctor has verified that the results of these pregnancy tests are negative. Females of child bearing potential with regular or no menstrual cycles must agree to have pregnancy tests every 7 days (weekly) for the first 28 days of study participation and then

every 28 days while on study, at treatment discontinuation, and 28 days following treatment discontinuation. If menstrual cycles are irregular, the pregnancy testing must occur weekly for the first 28 days and then every 14 days while on study, at treatment discontinuation, and at Days 14 and 28 following treatment discontinuation.

For subjects enrolled in Cohort B and Cohort C pregnancy prevention and testing will continue until 3 months after last dose of daratumumab.

**Blood Typing** - Blood typing of subjects is required during screening for subjects enrolling in Cohort B and Cohort C.

### ***Indirect Antiglobulin Test (IAT)***

Daratumumab interferes with the Indirect Antiglobulin Test (IAT), which is a routine pretransfusion test performed to identify a patient's antibodies to minor antigens so that suitable donor blood can be given for transfusion. Daratumumab does not interfere with ABO/RhD typing. CD38 is expressed at very low levels on erythrocytes. Daratumumab binds to the CD38 on erythrocytes, which results in a positive IAT (Indirect Coombs Test). This positive result masks the detection of antibodies to minor antigens and may prevent or delay blood banks from issuing donor blood for transfusion. This effect occurs during daratumumab treatment and for up to 6 months after treatment ends. Subjects will receive a patient identification wallet card for the study that includes the blood profile (ABO, Rh, and IAT or phenotyping) determined before the first infusion of daratumumab along with information on the IAT interference for healthcare providers/blood banks. Subjects are to carry this card throughout the treatment period and for at least 6 months after treatment ends. Blood banks can eliminate the daratumumab interference with IAT by treating reagent RBCs with dithiothreitol (DTT) ([Chapuy, 2015](#)).

Possible methods for blood banks to provide safe RBCs for transfusion to subjects receiving daratumumab include:

1. Providing ABO/RhD compatible, phenotypically (standard or extended phenotyping prior to daratumumab administration) or genotypically matched units
2. Providing ABO/RhD compatible, K-negative units after ruling out or identifying alloantibodies using DTT-treated reagent RBCs

Uncrossmatched, ABO/RhD compatible RBC units should be administered if transfusion is needed emergently as per local blood bank practice.

Despite daratumumab binding to CD38 on erythrocytes, no indication of clinically significant hemolysis has been observed in daratumumab studies. For additional details, refer to the Daratumumab Investigator's Brochure (IB).

### **Efficacy Assessments**

Disease progression status will be assessed by the Investigator at each treatment cycle and at treatment discontinuation. Tumor response including progressive disease will be assessed according to the IMWG uniform response criteria ([Durie, 2006](#)) and modified to add criteria for MR ([Kyle, 2009](#)). All treatment decisions will be made by the treating physician based on response as assessed using the mIMWG criteria (per [Appendix B](#)).

Daratumumab is a human IgG kappa monoclonal antibody that can be detected on both, the serum protein electrophoresis (SPEP) and immunofixation (IFE) assays used for the clinical

monitoring of endogenous M-protein. This can lead to false positive SPEP and IFE assay results for subjects with IgG kappa myeloma protein impacting initial assessment of complete responses by International Myeloma Working Group (IMWG) criteria. In subjects with persistent very good partial response, consider other methods to evaluate the depth of response.

Survival status will be collected for all subjects during the long-term follow-up phase.

All efficacy laboratory assessments will be performed and reviewed by the central laboratory. These efficacy assessments include laboratory tests used as part of standard care: Serum beta-2 microglobulin (at screening only), myeloma paraprotein protein electrophoresis and immunofixation, serum immunoglobulins, and serum free light chain assay.

Efficacy assessments are to be performed at the start of each new cycle. If a new cycle is delayed more than 7 days (but less than 28 days) from the protocol-defined 28-day dosing cycle, an unscheduled visit should be performed for efficacy assessments prior to initiation of the next cycle. If the delay is greater than 28 days, these efficacy assessments should be performed every 28 days ( $\pm 3$  days) until a new cycle can begin. For subsequent cycles following a delayed cycle, efficacy assessments should be performed at the start of each new cycle.

The efficacy assessments will be documented in the source documents and recorded on the eCRF.

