### ***Follow-up Phase***

All study subjects will enter the follow-up phase within 28 days of last dose of study medication. During follow-up, the following information will be collected from all subjects 4 times per year (every 3 months) for up to 5 years after the last subject is enrolled in each respective cohort: survival, SPM, subsequent anti-myeloma treatments (type of treatment, start and stop dates, best response whenever possible and date of progression).

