### ***Treatment Discontinuation***

Subjects will continue study treatment until the documentation of confirmed PD, intolerable toxicity, death, withdrawal of active participation/consent in the study, or loss to follow-up, or as long as they benefit from therapy according to the opinion of the responsible study investigator and discussed with the sponsor.

Subjects are not permitted to start any other anti-myeloma therapy before progression is confirmed or subject cannot tolerate study treatment. A treatment discontinuation visit will be required for all subjects who discontinue treatment.

- If POM is permanently discontinued, then the subject must be permanently discontinued from all study treatments.
- For Patients in Cohort B and Cohort C, if DARA is withheld or permanently discontinued, then POM, and LD-Dex dosing may be continued.
- If LD-dex dosing is withheld or permanently discontinued, then POM and DARA (for patients in Cohort B and Cohort C) dosing may be continued.

See dose administration guidance in Section 8.3.

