  - p Assessment/measurement at specified time-points only required if EMPs are present. If EMPs are clinically assessable, clinical assessment will be performed at screening, at every Cycle Day 1, and at treatment discontinuation. If EMPs are only assessable radiographically (x-ray and/or conventional [spiral] CT/MRI scan), scans are required at screening, at Cycle 3 Day 1, every 3 cycles thereafter (Cycle 6 Day 1, Cycle 9 Day 1, etc.) during treatment, at treatment discontinuation, and when clinically indicated to confirm response ( $\geq$  PR).
  - q A skeletal survey by x-ray will be performed at screening and when clinically indicated per the investigator's discretion. If a skeletal survey was performed within 60 days prior to the start of Cycle 1, it may be used for the screening assessment if approved by sponsor. Refer to [Appendix C](#) for detailed requirements.
  - r Response, including PD, will be assessed by investigators using the modified International Myeloma Working Group criteria ([Appendix B](#)). Response assessment should also be repeated at the time of response ( $\geq$  PR) or PD confirmation. The first response assessment will occur at Day 1 of Cycle 2.
  - s Subsequent anti-myeloma regimens: type of treatment, start and stop dates, date of progression and best response whenever possible.
  - t For Cohort A and Cohort B subjects who consent to participate in biomarker analysis may undergo collection of bone marrow aspirate and whole blood samples at screening, response assessment (confirm CR) and disease progression, and when clinically indicated. Additionally, whole blood samples will be collected at Day 1 of Cycle 3,5 and

treatment discontinuation for Cohort A and **C1D1, C1D8, C1D15, C2D1, C2D15, C3D1, C5D1 and treatment discontinuation** for Cohort B. For Cohort C, all subjects will provide bone marrow aspirate at screening and treatment discontinuation.

u For Cohort A and Cohort B subjects who consent to participate in biomarker analysis may undergo collection of normal tissue (which may include saliva samples) at screening only.

v For subjects enrolled in Cohort B, Quality of Life (QoL) measured with the descriptive system of the EQ-5D will be provided to each subject to complete on Day 1 of every cycle prior to any study treatment (POM, DARA, LD-dex) administration and at treatment discontinuation.

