### ***Assessment of Response***

Response, including PD, will be assessed using the mIMWG criteria ([Appendix B](#)) at Day 1 of each Cycle and at the treatment discontinuation visit.

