### ***Overall Survival and Subsequent Anti-MM Therapies***

During the follow-up period, survival status and subsequent therapies for MM must be collected and entered into the eCRF. All subjects will be assessed 4 times a year (every 3 months) to determine survival status for up to 5 years after the last subject is enrolled in each respective cohort. Primary cause of death (medical condition) is to be recorded in the eCRF and the subject's medical record. All subsequent therapies given for MM must be collected and entered into the eCRF.

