#### **10.6. Efficacy Analysis**

The primary efficacy analysis will be performed on both the ITT and EE populations. The exact binomial test will be used to test the hypothesis that the ORR for the Cohort A is greater than 16%. The final primary analysis on ORR will report exact 2-sided p-values with 95% Clopper-Pearson confidence intervals (Collett, 2003). For Cohort B point estimates of the ORR together with 95% confidence interval will be calculated using the normal approximation to the binomial distribution. Analysis for Cohort C will mirror the analysis for Cohort A except for a test of the hypothesis of an ORR greater than 25%.

The Kaplan-Meier procedures will be used to characterize the time-to-event curves (PFS, OS, TTP, and response duration) and the median and 95% confidence intervals of time to each of these events will be estimated. Univariate summary statistics will be provided for time to response. Progression-free survival and OS will be analyzed in the ITT as well as the EE populations. Other secondary efficacy endpoints will be analyzed in the ITT population only.

Analyses of PFS, OS, TTP, and response duration will be updated at the end of the long-term follow-up phase of the study.

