#### **Time to Progression**

Time to progression will be calculated as the time from start of treatment until PD (as determined by the site investigator based on the mIMWG criteria). Subjects not experiencing a documented progression will be censored at the time of their last response assessment (or at the time of trial enrollment if no assessment was conducted).

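### Scheduled disease assessment ends at treatment discontinuation, so subjects who stop without progression have no defined route to a later progression event in PFS, TTP or DoR

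*Combined protocol and SAP*

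**What the plan says.** Section 6 (Efficacy Assessments) sets the schedule: "Disease progression status will be assessed by the Investigator at each treatment cycle and at treatment discontinuation". Section 6 (Assessment of Response) agrees, placing the modified IMWG assessment "at Day 1 of each Cycle and at the treatment discontinuation visit". In Table 1 the rows for response assessment, serum and urine electrophoresis, free light chains and extramedullary plasmacytomas are all empty at the 28-day follow-up visit and throughout long-term follow-up.

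The 3-monthly follow-up (Protocol Summary, Follow-up Phase) collects survival, second primary malignancies and "subsequent anti-myeloma treatments (type of treatment, start and stop dates, best response whenever possible and date of progression". Table 1, footnote s, has the same item: "Subsequent anti-myeloma regimens: type of treatment, start and stop dates, date of progression and best response whenever possible". Section 6 (Overall Survival and Subsequent Anti-MM Therapies) says that "survival status and subsequent therapies for MM must be collected and entered into the eCRF" and names no disease assessment.

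Section 10.6 gives the censoring rule for TTP, with the same rule for PFS and a close equivalent for DoR: "Subjects not experiencing a documented progression will be censored at the time of their last response assessment". It also promises that "Analyses of PFS, OS, TTP, and response duration will be updated at the end of the long-term follow-up phase of the study".

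Stopping for reasons other than progression is foreseen. Section 12 lists adverse events, withdrawal from active participation and protocol violation among the reasons, and the discontinuation rules state: "If POM is permanently discontinued, then the subject must be permanently discontinued from all study treatments".

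**The concern.** PFS, TTP and DoR are stated secondary endpoints. Take a subject who permanently stops all study drugs for toxicity while in partial response or stable disease. The last scheduled assessment is the discontinuation visit, and that is where Section 10.6 censors the subject. No test is scheduled that could show the later relapse.

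The Kaplan-Meier estimate then relies on such subjects having the same later progression rate as those still treated and assessed. They have stopped the study drugs, for reasons that may reflect frailty or disease course, and Section 1 calls the disease relapsing and incurable. If their rate differs, the censoring is informative and the medians are biased. Even if it does not differ, those progression events are lost and precision suffers.

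New therapy is a second gap. Section 9.2 allows it once study treatment is discontinued, so it can start before progression. For ORR, Section 10.6 says what happens to responses after new therapy. For PFS, TTP and DoR it gives no rule.

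**Working it through.** **Step 1: is there any route to a post-treatment progression event?** The plan states no event count or precision for PFS, TTP or DoR, so there is no figure to reproduce. The check is to set what the endpoints need beside what is collected.

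| What the endpoint needs | What exists after discontinuation |
|---|---|
| PFS, TTP: progression determined by the investigator on modified IMWG criteria (10.6) | No scheduled assessment (Table 1; Section 6) |
| DoR: confirmed progression, or death (10.6) | No scheduled assessment; deaths are recorded |
| Two consecutive assessments for progression (Appendix B, Table 11, footnote a) | No scheduled tests |
| Central laboratory results (Protocol Summary, efficacy overview; Section 6) | No central samples scheduled |
| First progression on or after study therapy | A progression date listed as an attribute of a subsequent regimen |

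The last row is the only candidate route. A subject with no next regimen may have no such date. Where a date exists, it may be progression before the next regimen or on it. No criteria are named for it, and Section 10.6 does not mention it.

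**Step 2: what can the end-of-follow-up update add?** It can add progressions in subjects still on treatment at the earlier cut-off, and deaths after treatment to DoR. PFS counts deaths only on study treatment, so it does not gain those. For subjects who left without progression, the update has no scheduled disease data.

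**Step 3: how large could the effect be?** The following inputs are assumptions, because the documents give none for this trial:

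- L: on-treatment progression hazard, L = ln 2 / m, where m is the median estimated with censoring at discontinuation.
- f: share who stop before progression; stopping hazard g = L × f/(1 − f).
- h: ratio of the off-treatment to the on-treatment progression hazard.

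Censoring at discontinuation gives a Kaplan-Meier median of m. Under continued assessment the median t solves

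exp(−(L+g)t) + g[exp(−hLt) − exp(−(L+g)t)]/(L+g−hL) = 0.5.

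Example with m = 12 months, f = 0.30, h = 2: L = 0.0578, g = 0.0578 × 0.30/0.70 = 0.0248, L+g = 0.0825, hL = 0.1155. At t = 10.87 the first term is 0.408 and the second is 0.0248 × (0.285 − 0.408)/(0.0825 − 0.1155) = 0.092. They sum to 0.500. The reported 12.0 is too long by 12/10.87 − 1 = 10.4%.

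Error in the reported median, m/t − 1 (the same for any m):

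| f | h = 0.5 | h = 1 | h = 2 | h = 3 |
|---|---|---|---|---|
| 7% | −1.5% | 0 | +2.0% | +3.4% |
| 10% | −2.2% | 0 | +3.0% | +4.9% |
| 20% | −4.8% | 0 | +6.4% | +10.5% |
| 30% | −8.1% | 0 | +10.4% | +17.0% |

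At m = 12 and f = 0.30, the median under continued assessment is 10.87 months (h = 2), 10.25 (h = 3) or 13.05 (h = 0.5). At m = 4.6, the doublet PFS median cited in Section 1.2, the same f gives 4.17, 3.93 and 5.00.

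**Step 4: scale.** For pomalidomide plus low-dose dexamethasone in CC-4047-MM-002, Section 1.2 gives progression as the reason for discontinuation in 51% and adverse events in 7%, without stating the denominator. If all the other 49% had stopped without progression, an extreme reading, the overstatement would be 20% (h = 2) to 33% (h = 3). At 10-30%, the subjects concerned would number about 6-17 of 56 in Cohort A, 11-34 of 112 in Cohort B and 2-6 of 20 in Cohort C.

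**The case against.** A reader might infer that these subjects can never have a progression event and that their relapse is recorded nowhere. The documents do not support that. A progression date is collected in follow-up, and the PFS and TTP definitions do not require progression to occur on treatment. What can be shown is narrower: the field is undefined and not linked to the endpoints.

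A reader might also infer that the endpoints measure progression only while drug is being taken. Section 6 contradicts this, since efficacy assessments continue every 28 days when a cycle is delayed by more than 28 days. Assessment ends at permanent discontinuation, not at a pause. Stopping daratumumab or dexamethasone alone need not end treatment.

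Nor is the direction of bias established. Subjects who stop in deep response, or who start effective new therapy, could progress more slowly, and the sign then reverses. With only the 7% adverse-event figure as a guide, the error is 2-3% at a doubled or tripled hazard, or 0.09-0.15 months on a median of 4.6. These analyses are descriptive, with no planned test.

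All of this stands and limits the claim. It does not remove the gap: no scheduled assessment, no defined use for the follow-up date and no rule at new therapy. It is also fair that an added eCRF field will not match on-treatment progression, given the two-assessment rule, central testing and the daratumumab interference assay. That is a cost of the fix.

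**Conclusion.** The concern holds in limited form. Subjects who permanently stop without progression have no scheduled disease assessment and no defined route to a later progression event in PFS, TTP or DoR. The planned update has no scheduled progression data for them. It would be too strong to say that five years of follow-up cannot help: the update still adds events in subjects on treatment, adds deaths to DoR, and could use follow-up progression dates if they were defined for that purpose.

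The likely direction is overly long times, because these subjects have stopped study therapy for a relapsing disease, but this is a judgement. The illustrated range, about 3-17% too long, none, or up to about 8% too short, rests on constant hazards, 10-30% stopping without progression, and hazard ratios of 2-3, 1 and 0.5 respectively. The model covers time to progression without deaths, so it carries over to PFS and DoR only approximately. ORR is not touched. The change should be made because it is cheap, not because the main conclusion is at risk.

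**What to change.** 1. In the Protocol Summary (Follow-up Phase), Section 6 (Overall Survival and Subsequent Anti-MM Therapies) and Table 1 footnote s: for subjects who stop without progression, record at the existing 3-monthly contact the date of first progression before any new anti-myeloma therapy. Base it on investigator modified IMWG assessment of routine local results, and state that local results are acceptable here. Continue until progression, new therapy or death. State in Section 10.6 that this progression counts in PFS, TTP and DoR. Apply it prospectively to Cohort C and to subjects in Cohorts A and B still in follow-up, and retrospectively where records allow.
2. For all cohorts, add to Section 10.6 a sensitivity analysis of PFS, TTP and DoR that counts the start of subsequent anti-myeloma therapy without prior progression as an event. The dates are already collected.
3. If item 1 is not adopted, label the main PFS, TTP and DoR results as based on progression assessed up to treatment discontinuation.

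Cost: a defined eCRF item at a contact that already takes place, amended text and one further analysis; no added visits or study procedures. Post-treatment progression dates will be coarser (contacts every 84 ± 14 days, local tests) and incomplete for earlier leavers. Reported PFS, TTP and DoR may become slightly shorter.

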### ***Eastern Cooperative Oncology Group Performance Status***

Eastern Cooperative Oncology Group (ECOG) Performance Status will be assessed at screening, at Day 1 of every Cycle, and at treatment discontinuation. See [Appendix E](#) for the ECOG Performance Status Scale.

### ***Laboratory Assessments for Efficacy Parameters***

All laboratory assessments for efficacy parameters will be performed by central laboratory.

- **Serum beta-2 microglobulin.** The serum beta-2 microglobulin sample will be collected at screening only.
- **Myeloma Paraprotein (M-Proteins) Protein Electrophoresis.** Serum protein electrophoresis (quantified from the serum protein electrophoresis [SPEP] test) and urine protein electrophoresis (quantified from the urine protein electrophoresis [UPEP] test performed on the 24-hour urine collection), will be performed at screening, at every cycle on Day 1, and at treatment discontinuation. If a response or PD is noted based on SPEP and/or UPEP results, SPEP and UPEP tests should be repeated as soon as possible to confirm the response ( $\geq$  PR) or PD.
- **Myeloma Paraprotein (M-Proteins) Immunofixation.** Serum and urine immunofixation (IFE) tests are performed at screening to identify the immunoglobulin subtype of MM and thereafter are required to be performed whenever M-protein is undetectable in both serum and urine by protein electrophoresis studies. Serum and urine IFE tests should also be performed at the time of response confirmation for CR.
- **Serum Immunoglobulins** assessment will be performed at screening and at every cycle on Day 1, at treatment discontinuation, and at the time of response confirmation

for CR. All subjects will be evaluated for IgG, IgA, and IgM. Testing for IgE and IgD is only required for subjects with the respective (IgE or IgD) subtype.

- **Serum Free Light Chain** assay will be performed at screening, at every cycle on Day 1, at treatment discontinuation, and at the time of response confirmation for CR.

A 24-hour urine sample obtained as a standard of care assessment prior to informed consent can be utilized for this study if it was performed  $\leq 7$  days prior to the Screening Visit and meets the protocol requirements for collection and analysis. Additionally, if screening visit results are  $\leq 7$  days prior to enrollment, these laboratory assessments are not required to be repeated at Cycle 1 Day 1.

